7.4.1.2. Termination of the Infusion

The infusion should be terminated and NOT restarted if any of the following AEs occur:

- anaphylaxis
- laryngeal/pharyngeal edema
- severe bronchospasm
- chest pain
- seizure
- severe hypotension
- other neurological symptoms (confusion, loss of consciousness, paresthesia, paralysis, etc.)
- any other symptom or sign that, in the opinion of the investigator, warrants discontinuation of the infusion

7.5. Method of Treatment Assignment

Each patient who signs the informed consent form (ICF) will be assigned a patient number and tracked centrally as described in the Interactive Web Response System (IWRS) manual.

Eligible patients will be enrolled sequentially as confirmed and tracked by the sponsor, until each group is filled per protocol criteria. Details on treatment assignment can be found in the IWRS manual.

7.5.1. Blinding

This is an open-label study; no blinding will be employed.

7.6. Treatment Logistics and Accountability

7.6.1. Packaging, Labeling, and Storage

Open-label study drug will display the product lot number on the label.

Study drug will be stored at the site at a temperature of 2° to 8°C; storage instructions will be provided in the pharmacy manual.

7.6.2. Supply and Disposition of Treatments

Study drug will be shipped at a temperature of 2° to 8°C to the investigator or designee at regular intervals or as needed during the study. At specified time points during the study (eg, interim site monitoring visits), at the site close-out visit, and following drug reconciliation and documentation by the site monitor, all opened and unopened study drug will be destroyed or returned to the sponsor or designee.

7.6.3. Treatment Accountability

All drug accountability records must be kept current.

The investigator must be able to account for all opened and unopened study drug. These records should contain the dates, quantity, and study medication

- dispensed to each patient,
- returned from each patient (if applicable), and
- disposed of at the site or returned to the sponsor or designee.

All accountability records must be made available for inspection by the sponsor and regulatory agency inspectors; photocopies must be provided to the sponsor at the conclusion of the study.

7.6.4. Treatment Compliance

Cemiplimab will be administered at the study site and recorded on the electronic case report form (eCRF). All dosing records for each patient will be kept by the site. All drug compliance records must be kept current and made available for inspection by the sponsor and regulatory agency inspectors.

7.7. Concomitant Medications and Procedures

Any treatment administered from the time of informed consent until 30 days after the last study treatment will be considered concomitant treatment. This includes medications and other therapies for which administration started before the study and will continue during the study, as well as any therapies started in the follow-up period (approximately 6 months) to treat a study drug-related AE. All concomitant treatments must be recorded in the study CRF with the generic name, dose, dose unit, frequency, indication, and start/stop date, as appropriate.

7.7.1. Prohibited Medications and Procedures

While participating in this study, a patient may not receive any standard or investigational agent for treatment of a tumor other than cemiplimab as monotherapy. After communication with the sponsor, focal palliative treatment (eg, radiation) would be allowed for local control of a tumor once a patient has completed 24 weeks of study treatment. Patients must not receive live vaccines during the study and up to 5 half-lives after the last dose of study drug. Any other medication which is considered necessary for the patient's welfare, and which is not expected to interfere with the evaluation of the study drug, may be given at the discretion of the investigator.

Patients using immunosuppressive doses (>10 mg per day of prednisone or equivalent) of systemic corticosteroids other than for corticosteroid replacement will not be eligible for the study. It is recommended that patients do not receive systemic corticosteroids such as hydrocortisone, prednisone, prednisolone (Solu-Medrol[®]) or dexamethasone (Decadron[®]) at any time throughout the study except in the case of a life-threatening emergency and/or to treat an irAE. Physiologic replacement doses of systemic corticosteroids are permitted, even if >10 mg/day prednisone equivalents. A brief course of corticosteroids for prophylaxis (eg, contrast dye allergy) or for treatment of non-autoimmune conditions (eg, delayed-type hypersensitivity reaction caused by contact allergen) is permitted.

Note: Bisphosphonates and denosumab are not prohibited.

7.7.2. Surgery

For patients with locally advanced target lesions that are considered unresectable at baseline, but are subsequently deemed resectable during the course of the study due to tumor response to cemiplimab, curative intent surgery may be allowed, but must be discussed with the medical monitor prior to any surgical procedure. (This statement does not apply to patients in emergency life-threatening situations that require immediate surgery). Patients with inoperable BCC at baseline who are rendered operable with clear margins will be deemed to have experienced PR.

If during the course of the study a patient develops new cutaneous lesions that are suspected to be a non-melanoma skin cancer other than BCC (eg, CSCC), removal of the lesion and continued treatment on study may be allowed after discussion with the medical monitor.

7.7.3. Radiation Therapy

Radiation therapy is not part of the study regimen. Patients for whom radiation therapy is planned are not eligible. If, during the course of the study, a patient develops a symptomatic lesion for which palliative radiation therapy is deemed appropriate by the investigator, this will be deemed PD and generally the patient would be removed from study. Palliative radiation therapy may be allowed in certain circumstances in patients who have been on study for at least 24 weeks (see Section 7.7.1). Such cases must be discussed with the medical monitor prior to any radiation therapy if the investigator feels that restarting cemiplimab after radiation is in the best interest of the patient. The patient will be deemed to have experienced disease progression if radiation therapy is instituted, but will be followed for OS.

8. STUDY SCHEDULE OF EVENTS AND PROCEDURES

8.1. Schedule of Events

Study assessments and procedures in the treatment periods are presented in [Table 4](#) and [Table 5](#). Study assessments and procedures in the follow-up period are presented in [Table 6](#). Study visits can be scheduled so as not to fall on weekends or holidays, after discussion and approval by the Sponsor.

Table 4: Schedule of Events for Treatment Cycles 1 - 5 (9-Week Cycles)

Study Procedure	Screening	Cycle 1				Cycles 2-5 ¹				End of Study
		1	22±3	43±3	64±3	1 ²	22±3	43±3	64±3	
Visit Days	-28 to -1									30 days after last dose cemiplimab ³
Clinical Assessments and Study Treatment										
Informed Consent ⁴	X ⁴									
[REDACTED]	X									
Medical/Oncology History	X									
Complete Physical Examination, Neurological Exam, and ECOG PS ⁵	X	X				X				X
Physical Examination (Limited) ⁶			X	X			X	X		
12-Lead ECG ⁷	X	X				X				X
Vital Signs and Weight ⁸	X	X	X	X		X	X	X		X
Height	X									
Brain MRI ⁹	X									
350 mg cemiplimab Q3W IV		X	X	X		X	X	X		
Laboratory Tests										
Hematology ¹⁰ and Blood Chemistry ¹¹	X	X	X	X		X	X	X		X
Serum HCG ≤72 Hour Predose ¹²	X									
Urine Pregnancy Test										X ¹³
Urinalysis ¹⁴	X	X				X				X
aPTT; INR		X								X
HBV, HCV, HIV	X									
Immune Safety and PK Blood Samples										
RF and ANA		X				X				X
TSH and CRP		X				X				X
ADA ¹⁵		X ¹⁵		X		X ¹⁵				X
Cemiplimab PK/Drug Conc ¹⁶		X	X	X		X				X
Pathology and Exploratory Biomarker Research Samples										
Archived tissue for histological confirmation of BCC ¹⁷	X									
Tumor biopsies for Group 2 ¹⁸	X		X							
[REDACTED]		X								

Study Procedure	Screening	Cycle 1				Cycles 2-5 ¹				End of Study
Visit Days	-28 to -1	1	22± 3	43± 3	64±3	1 ²	22±3	43±3	64±3	30 days after last dose cemiplimab ³
Response Imaging and Other Assessments										
CT/MRI and/or digital photography ¹⁹	X		X ²⁰		X				X	X
EORTC QLQ-C30, Skindex-16 ²¹		X				X				X
Concomitant medications ²²	X	X	X	X	X	X	X	X	X	X
Adverse Events ²³	← continuous monitoring→									

8.1.1. Footnotes for the Schedule of Events for Treatment Cycles 1 – 5 (9-Week Cycles) – Table 4

ADA=anti-drug antibody; AE=adverse event; ANA=antinuclear antibody; ECOG PS=Eastern Cooperative Oncology Group Performance Status; EOS=end of study; HBV=hepatitis B virus; HCG=human chorionic gonadotropin; HCV=hepatitis C virus; HIV=human immunodeficiency virus; INR=International Normalized Ratio; MRI=magnetic resonance imaging; RF= rheumatoid factor; TSH=thyroid-stimulating hormone

1. There are 5 treatment cycles of 9 weeks in this table, followed by 4 treatment cycles of 12 weeks in the subsequent table. The maximum number of treatment cycles is 9 (planned 93 weeks total).

2. Should occur at least 59 days from day 1 of previous cycle, and no sooner than 18 days after the previous dose.

(1) The EOS visit is for patients who experience PD requiring study discontinuation in cycles 1 through 5. This visit should occur 30 days (allowed window: 21 to 42 days) after the last dose of cemiplimab. The only posttreatment assessment that can occur outside of this timeframe is the posttreatment biopsy (required in Group 2) that can be obtained at any time within 28 days of last dose of cemiplimab.

(2) Patients who complete the required events in Table 4 and Table 5 (excluding the EOS visit) with any status other than PD (eg, CR, PR, or SD) will go on to complete the assessments for follow up in Table 6.

3. Patients who do not experience PD do not need to complete the EOS visit at end of cycle 9. Patients will be followed quarterly for survival and tumor treatment status, if available.

4. Informed consent must be provided before the initiation of screening procedures, and must be obtained within 45 days prior to cycle 1/day 1. All screening assessments must be performed within 28 days prior to cycle 1/day 1 (with exception for brain MRI according to footnote 9, as per below). Assessments performed as part of standard of care that fall within the screening window but before informed consent is obtained may be used for screening, and need not be repeated for enrollment eligibility.

5. Complete physical examination includes head and neck, lungs, heart, abdomen, lymph nodes, extremities, and skin. A brief neurologic examination should also be performed. The exam may be performed ≤ 72 hours prior to study treatment. Complete physical exam must be accompanied by assessment and documentation of ECOG Performance Status.
6. Limited physical exam includes lungs, heart, abdomen, and skin.
7. A 12-lead ECG should be recorded at screening, and 30 minutes (± 10 minutes) after end of infusion at day 1 visits during cycle 1 and cycle 3, and at end of study. The patient should be relaxed and in a recumbent or semi-recumbent position at least 5 minutes before recording an ECG.
8. Vital signs include temperature, resting blood pressure, pulse, and respiration. Vital signs will be assessed and documented prior to the cemiplimab infusion, and then approximately 15 minutes (± 10 minutes) after the completion of the cemiplimab infusion. Refer to Section 8.2.3.1 for more information.
9. Brain MRI with gadolinium is required at screening if not performed in the prior 60 days. Brain scans during the treatment and follow-up periods are required if there is a prior history of lesions present at screening or as clinically indicated. A brain CT with iodinated contrast may be performed if an MRI with gadolinium is contraindicated.
10. Hematology samples may be collected ≤ 72 hours prior to study treatment. Refer to Section 8.2.3.6 for the hematology panel.
11. Chemistry samples may be collected ≤ 72 hours prior to study treatment. Refer to Section 8.2.3.6 for the chemistry panel.
12. Predose β -HCG (serum) at screening up to 72 hours prior to first administration. Subsequent pregnancy tests may be urine β -HCG. Serum pregnancy test and urine pregnancy test are requirements for women of child bearing potential only.
13. Urine pregnancy test should be done cycle 1 day 43, cycle 2 day 22, cycle 3 days 1 and 43, cycle 4 day 22, cycle 5 day 1.
14. Urinalysis samples may be collected ≤ 72 hours prior to study treatment. Refer to Section 8.2.3.6 for the urinalysis panel.
15. ADA samples are collected prior to treatment on day 1 and day 43 of cycle 1, and prior to treatment on day 1 of cycles 3 and 5. For patients who complete cycles 1 through 5 and begin follow-up, an ADA sample is collected at end of study (30 days after last dose).
16. Blood samples for PK will be collected at pre-infusion and at end-of-infusion (within 10 minutes after the end of infusion) on days 1, 22, and 43 cycle 1, and on day 1 of cycles 2 through 5. For patients who discontinue treatment during cycles 1 through 5, a PK sample is collected 30 days after last dose of study drug.
17. Section 8.2.1 provides the requirements for documentation of histologic confirmation of diagnosis of BCC.

18. For Group 2 patients only: Exploratory tumor biopsies (paired) are required at baseline and on cycle 1 day 22 (± 3 business days), and at progression (see [Appendix 5](#)). Optional tumor biopsies (paired “Response Biopsies”) should be performed at any response assessment in which there is indeterminate-appearing skin regarding malignant versus benign status (see [Appendix 5](#)). Tumor biopsies should also be collected for histologic confirmation of complete response in any patient for whom the clinical impression is complete response, as well as at progression. Biopsied lesions must be annotated and photographed as per [Appendix 6](#).
19. The same method (CT with iodinated contrast or MRI with gadolinium) and/or digital medical photography used at baseline should be used throughout the study. Imaging requirements differ for patients in Group 1 and Group 2, and are provided in [Section 8.2.2](#). For the day 22 exploratory tumor biopsy for Group 2 patients, the purpose of the photography is to demonstrate the location of the biopsy. Formal response assessment is not planned for the day 22 photo. In [Table 4](#), the rows for day 64 are intended as visual reminders for end-of-cycle tumor assessments. cemiplimab treatment occurs on day 1 of the subsequent cycle.
20. The “X” for day 22 in cycle 1 pertains to digital medical photography of Group 2 patients (not Group 1) who undergo Exploratory Biopsies on day 22. The day 22 photos are annotated to demonstrate biopsy locations, and are not intended for tumor response assessments. Scheduled tumor response assessments during cycles 1 to 5 are every 9 weeks.
21. If the Skindex-16 translation is not available for a specific language this can be omitted.
22. Concomitant medication recording will be done at every visit.
23. Adverse event recording will be ongoing throughout the course of the study, using NCI-CTCAE v4.03.

Table 5: Schedule of Events for Cycle 6 – 9 (12–Week Cycles)

Study Procedure	Cycles 6 - 9					End of Study
	1±3 ¹	22±3	43±3	64±3	85±3	30 days after last dose cemiplimab ²
Clinical Assessments and Study Treatment						
Complete Physical Examination, Neurological Exam, and ECOG PS ³	X					X
Physical Examination (Limited) ⁴		X	X	X		
12-Lead ECG ⁵	X					X
Vital Signs and Weight ⁶	X	X	X	X		X
350 mg cemiplimab Q3W IV	X	X	X	X		
Laboratory Tests						
Hematology ⁷ and Blood Chemistry ⁸	X	X	X	X		X
Pregnancy Test (serum or urine)	X		X			X
Urinalysis ⁹	X		X			X
aPTT; INR						X
Immune Safety and PK Blood Samples						
RF and ANA	X					X
TSH and CRP	X					X
ADA ¹⁰	X					X
Cemiplimab PK/Drug Conc ¹¹	X					X
Response Imaging and Other Assessments						
CT/MRI and/or digital photography ^{12,13}					X	X
EORTC QLQ-C30, Skindex-16 ¹⁴	X					X
Concomitant medications ¹⁵	X	X	X	X	X	X
Adverse Events ¹⁶	← continuous monitoring→					

8.1.2. Footnotes for the Schedule of Events for Treatment Cycles 6 – 9 (12-Week Cycles) – Table 5

ADA=anti-drug antibody; AE=adverse event; ANA=antinuclear antibody; ECOG PS=Eastern Cooperative Oncology Group Performance Status; EOS=end of study; HBV=hepatitis B virus; HCG=human chorionic gonadotropin; HCV=hepatitis C virus; HIV=human immunodeficiency virus; INR=International Normalized Ratio; MRI=magnetic resonance imaging; RF= rheumatoid factor; TSH=thyroid-stimulating hormone

1. Should occur at least 59 days from the previous day 1 of cycle 5 (for cycle 6), or 81 days from day 1 of previous cycle (for cycles 7 – 9), and no sooner than 18 days after the previous dose.
 - (1) The EOS visit is for patients who experience PD requiring study discontinuation in cycles 6 through 9. This visit should occur 30 days (allowed window: 21 to 42 days) after the last dose of cemiplimab. The only posttreatment assessment that can occur outside of this timeframe is the post treatment biopsy (required in Group 2) that can be obtained at any time within 28 days of last dose of cemiplimab.
 - (2) Patients who complete the required events in [Table 4](#) and [Table 5](#) (excluding the EOS visit) with any status other than PD (eg, CR, PR, or SD) will go on to complete the assessments for follow up in [Table 6](#).
2. Patients who do not experience PD do not need to complete the EOS visit at end of cycle 9. Patients will be followed quarterly for survival and tumor treatment status, if available
3. Complete physical examination includes head and neck, lungs, heart, abdomen, lymph nodes, extremities, and skin. A brief neurologic examination should also be performed. The exam may be performed ≤ 72 hours prior to study treatment. Complete physical exam must be accompanied by assessment and documentation of ECOG Performance Status.
4. Limited physical exam includes lungs, heart, abdomen, and skin.
5. A 12-lead ECG should be recorded at screening, and 30 minutes (± 10 minutes) after end of infusion at day 1 visits during cycle 6 and cycle 9, and at end of study. The patient should be relaxed and in a recumbent or semi-recumbent position at least 5 minutes before recording an ECG.
6. Vital signs include temperature, resting blood pressure, pulse, and respiration. Vital signs will be assessed and documented prior to the cemiplimab infusion, and then approximately 15 minutes (± 10 minutes) after the completion of the cemiplimab infusion.
7. Hematology samples may be collected ≤ 72 hours prior to study treatment. Refer to Section [8.2.3.6](#) for the hematology panel.
8. Chemistry samples may be collected ≤ 72 hours prior to study treatment. Refer to Section [8.2.3.6](#) for the chemistry panel.

9. Urinalysis samples may be collected ≤ 72 hours prior to study treatment. Refer to Section 8.2.3.6 for the urinalysis panel.
10. ADA samples are collected prior to treatment on day 1 of cycles 6 through 9. For patients who discontinue treatment during cycles 6 through 9, an ADA sample is collected 30 days after last dose of study drug.
11. Blood samples for PK will be collected on day 1 of cycles 6 through 9 at pre-infusion and at end-of-infusion (within 10 minutes after the end of infusion). For patients who discontinue treatment during cycles 6 through 9, a PK sample is collected 30 days after last dose of study drug.
12. The same method (CT with iodinated contrast or MRI with gadolinium) and/or digital medical photography used at baseline should be used throughout the study. Imaging requirements differ for patients in Groups 1 and 2, and are provided in Section 8.2.2. In Table 5, the row for day 85 is intended as a visual reminder for end-of-cycle tumor assessment. Cemiplimab treatment occurs on day 1 of the subsequent cycle.
13. For Group 2 patients only: Optional tumor biopsies (paired “Response Biopsies”) should be performed at any response assessment in which there is indeterminate-appearing skin regarding malignant versus benign status (see Appendix 4). Tumor biopsies should also be collected for histologic confirmation of complete response in any patient for whom the clinical impression is complete response, as well as at progression. Biopsied lesions must be annotated and photographed as per Appendix 5.
14. If the Skindex-16 translation is not available for a specific language this can be omitted
15. Concomitant medication recording will be done at every visit.
16. Adverse event recording will be ongoing throughout the course of the study, using NCI-CTCAE v4.03.

Table 6: Schedule of Events for Follow-up (After 9 Cycles of Treatment)

Study Procedure Visit	Follow-up 1	Follow-up 2	Follow-up 3	Follow-up 4	Follow-up 5	Follow-up 6	Follow-up 7 ¹	Extended Follow-up
Time point (Day)	Cycle 9 visit + 28 ± 7 days	Follow-up 1 + 28 ± 7 days	Follow-up 2 + 28 ± 7 days	Follow-up 3 + 28 ± 7 Days	Follow-up 4 + 28 ± 7 days	Follow-up 5 + 28 ± 7 days	Follow-up 6 + 28 ± 7 days	Every 4 months for 1 year ¹³
Complete Physical examination and neurological exam ²	X	X	X	X	X	X	X	X
ECOG Status	X	X	X	X	X	X	X	X
Vital Signs ³	X	X	X	X	X	X	X	X
Weight	X	X	X	X	X	X	X	X
Laboratory Tests								
Hematology ^{4,5}	X							
Blood chemistry ^{4,5,6}	X							
Urine or serum pregnancy test ^{5,7}	X	X	X	X	X	X		
Urinalysis ^{5,8}	X							
Immune Safety Assays								
RF ⁵	X							
ANA ⁵	X							
TSH ⁵	X							
CRP ⁵	X							
PK Drug Conc/ADA Sample								
Cemiplimab PK/Drug Conc ⁹	X			X			X	
ADA sample ⁹	X						X	
Pathology Samples								
Tumor biopsy ⁵	←===== At Time of Progression =====→							
Tumor Assessments								
CT/MRI (chest/abdomen/pelvis) And/or digital photography ¹⁰		X		X			X	X

Other Clinical Assessments								
Concomitant medications ¹¹	X							
Adverse events ¹²	←=====							

8.1.3. Footnotes for the Schedule of Events for Follow-up (After 9 Cycles of Treatment) – Table 6

ADA=anti-drug antibody; AE=adverse event; ANA=antinuclear antibody; CRP=C-reactive protein; CT=computed tomography; ECOG=Eastern Cooperative Oncology Group; MRI=magnetic resonance imaging; RF= rheumatoid factor; TSH=thyroid-stimulating hormone.

1. After completion of this schedule of events, patients will be followed quarterly for survival and tumor treatment status, if available.
2. Complete physical examination includes head and neck, lungs, heart, abdomen, lymph nodes, extremities, and skin. A brief neurologic examination should also be performed. Complete physical exam must be accompanied by assessment and documentation of ECOG Performance Status.
3. Vital signs include temperature, resting blood pressure, pulse, and respiration.
4. Refer to Section 8.2.3.6 for the hematology panel.
5. At time of progression, the EOS tumor biopsy should be obtained for all patients in Group 2. Blood samples for laboratory tests (hematology, blood chemistry, urine pregnancy test, urinalysis) and immune safety (RF, ANA, TSH, CRP) are also obtained at time of progression (within 28 days of the imaging study that documented progression) according to the EOS assessment schedule (Table 4 and Table 5).
6. Refer to Section 8.2.3.6 for the chemistry panel.
7. Pregnancy tests may be urine β -HCG or serum.
8. Refer to Section 8.2.3.6 for the urinalysis panel.
9. Cemiplimab PK samples will be collected at follow-up visits 1, 4, and 7. ADA samples will be collected at follow-up visits 1 and 7. ADA is not required at the EOS visit if it was collected at follow-up visit 1. PK is not required at the EOS visit if it was collected at follow-up visit 1 and follow-up visit 4.
10. The same method (CT/MRI) and/or digital medical photography used at baseline should be used throughout the study. Scans linked to follow-up visits are required only if PD has not been confirmed previously while on study. CT/MRI imaging will be obtained within 14 days prior to the follow-up visit, so that the disease status is known at the time of the visit. Digital medical photography may be obtained within 14 days prior to visit, or on the day of the visit, and response status (CR, PR, SD, PR) will guide whether the visit is to be treated as a follow-up visit or as the EOS visit.

11. Concomitant medications should be recorded from the date of informed consent through 30 days after last dose of study drug. Any drug started to treat a study drug-related AE during the follow-up will also be recorded. In addition, any cancer treatments should be recorded from the day of informed consent until 105 days (5 half-lives) after the administration of the last dose of cemiplimab. Any AE assessed as related to study treatment and persisting after 105 days (5 half-lives) post last dose should be reported until resolution to baseline or grade ≤ 1 .
12. Nonserious AE and SAE data will be collected from the day of informed consent until 30 days after the last dose of cemiplimab. Any AE assessed as related to study treatment and persisting after 105 days (5 half-lives) post-last dose should be reported until resolution to baseline or grade ≤ 1 .
13. Patients who do not experience PD will be followed for an additional 1 year with assessments every 4 months.

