8.1.4. Follow-up

Patients who discontinue study treatment due to PD should return to the clinic 30 days (range: 21 to 42 days) after the last study treatment to complete the EOS assessments indicated in [Table 4](#) (same as in [Table 5](#)), as appropriate. After the EOS visit, patients with PD should be followed for survival status until death, loss to follow-up, or study termination by the sponsor.

For all patients in Group 2, tumor biopsies ([Appendix 4](#)) should be obtained at time of progression, whether progression occurs in cycles 1 through 9 or during follow-up (after cycle 9).

Patients who discontinue study treatment due to reasons other than PD (eg, toxicity, confirmed CR after 45 weeks) should continue follow-up to complete all assessments in [Table 6](#) until PD or completion of follow-up visits 1 to 7 and extended follow-up ([Table 6](#)). After this time, patients will be followed quarterly for survival and tumor treatment status, if available, until death. Survival follow-up status may be determined at clinic visits or via telephone contact with the patient, a family member of the patient, or the physician.

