9.4. Recording and Reporting Adverse Events

9.4.1. Adverse Events

The investigator (or designee) will seek information on AEs at each patient contact, and record all AEs that occur from the time the informed consent is signed until 105 days (5 half-lives) after the end of study treatment. Prior to initiation of study treatment, only the following categories of AEs should be reported on the AE CRF:

- SAEs
- Non-SAEs associated with a protocol-mandated intervention (eg, AEs related to an invasive procedure such as a biopsy)

Other AEs that occur prior to first treatment should be reported on the medical history CRF.

All AEs after initiation of study treatment and until 105 days (5 half-lives) after the last study treatment, regardless of relationship to study treatment, will be reported on the AE CRF.

Information on follow-up for AEs is provided in Section 9.4.6. Laboratory, vital signs, or ECG abnormalities are to be recorded as AEs as outlined in Section 9.4.5.

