9.4.2. Serious Adverse Events

All SAEs, regardless of assessment of causal relationship to study drug, must be reported to the sponsor (or designee) within 24 hours. Refer to the study reference manual for the procedure to be followed.

Information not available at the time of the initial report must be documented in a follow-up report. Substantiating data such as relevant hospital or medical records and diagnostic test reports may also be requested.

In the event the investigator is informed of an SAE that occurs until 105 days (5 half-lives) after the last dose of study treatment, only those SAEs or other AEs of concern deemed by the investigator to be related to study treatment will be reported to the sponsor. The investigator should make every effort to obtain follow-up information on the outcome of a treatment-related SAE until the event is considered chronic and/or stable.

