9.4.6. Follow-up

Information for any non-SAE that starts during the treatment period or within 105 days (5 half-lives) after last treatment will be collected from the time of the event until resolution of the event, or until the patient's last study visit, whichever comes first.

Serious adverse event information will be collected until the event is considered chronic and/or stable.

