10.4.5.1. Adverse Events

Definitions

For safety variables, 3 observation periods are defined:

- The pretreatment period is defined as the time from signing the ICF to before the first dose of study drug.
- The on-treatment period is defined as the time from first dose of study drug to 105 days after the last dose of study drug.
- The post-treatment period is defined as the time starting 1 day after the on-treatment period.

Treatment-emergent adverse events (TEAEs) are defined as AEs that are not present at baseline or represent the exacerbation of a pre-existing condition during the on-treatment period and treatment-related AEs that occurs any time after the first cemiplimab dose.

Note regarding retreatment: For patients who receive cemiplimab as retreatment, which starts more than 45 days after their last regular cemiplimab treatment, the on-treatment period ends at the earlier day of 105 days after the last regular cemiplimab dose and the day before their first cemiplimab retreatment dose. Cemiplimab retreatment that starts within 45 days after the last regular cemiplimab dose will be considered as regular cemiplimab treatment.

Analysis

All AEs reported in this study will be coded using the currently available version of the Medical Dictionary for Regulatory Activities (MedDRA[®]). Coding will be to lowest level terms. The verbatim text, the preferred term (PT), and the primary system organ class (SOC) will be listed.

Summaries of all TEAEs by group will include:

- The number (n) and percentage (%) of patients with at least 1 TEAE by SOC and PT
- TEAEs by severity (NCI-CTCAE, version 4.03 grade), presented by SOC and PT
- TEAEs by outcome
- TEAEs by relationship to experimental treatment (related, not related), presented by SOC and PT

Deaths and other SAEs will be listed and summarized by group.

Events of NCI-CTCAE Grade 3 and Grade 4 severity will be summarized by group.

Treatment-emergent adverse events leading to permanent treatment discontinuation will be listed and summarized by group.

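### Table 6 footnote 12 stops AE and SAE collection 30 days after the last dose, while Section 9.4 and the TEAE definition run to day 105; Section 9.4.2 also contradicts itself on SAE reporting

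*Protocol*

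**What the plan says.** **Collection window**

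- Protocol 8.1.3, Table 6 footnote 12: "Nonserious AE and SAE data will be collected from the day of informed consent until 30 days after the last dose of cemiplimab". Its next sentence deals with related AEs that persist beyond day 105.
- Protocol 9.4.1 tells the investigator to "record all AEs that occur from the time the informed consent is signed until 105 days (5 half-lives) after the end of study treatment", and repeats that this applies whatever the relationship to treatment.
- Protocol 9.4.6: "Information for any non-SAE that starts during the treatment period or within 105 days (5 half-lives) after last treatment will be collected". SAP 4.5.1 also records AEs to day 105.
- Table 4 footnote 23 and Table 5 footnote 16 set no 30-day stop: "Adverse event recording will be ongoing throughout the course of the study, using NCI-CTCAE v4.03".

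**Analysis window**

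- Protocol 10.4.5.1: "The on-treatment period is defined as the time from first dose of study drug to 105 days after the last dose of study drug". SAP 5.9.1 uses the same period, shortened if new systemic anticancer therapy or later retreatment begins.

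**Who is followed under Table 6**

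- Patients who complete treatment without progression and, under protocol 8.1.4, others as well: "Patients who discontinue study treatment due to reasons other than PD (eg, toxicity, confirmed CR after 45 weeks) should continue follow-up".

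**Reporting to the sponsor**

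- Protocol 9.4.2 opens with: "All SAEs, regardless of assessment of causal relationship to study drug, must be reported to the sponsor (or designee) within 24 hours". A later sentence, on SAEs occurring until 105 days after the last dose, says "only those SAEs or other AEs of concern deemed by the investigator to be related to study treatment will be reported to the sponsor". SAP 4.5.1 applies the related-only rule to events later than 105 days.

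**The concern.** The TEAE tables treat a patient as at risk until 105 days after the last dose. If a site stops recording at day 30 because footnote 12 says so, events starting on days 31 to 105 never reach the database, yet the patient still counts as observed. TEAE and serious TEAE numerators, and the attribution of a late fatal AE, could then be too low, and differently so across sites, although each site could claim to be following the protocol.

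The patients concerned include those who stopped for toxicity. Protocol 9.4.3 itself warns that immune-related events can appear months after the last dose.

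The 9.4.2 conflict is a separate problem. It decides which late SAEs reach the sponsor promptly. It does not by itself remove events from the TEAE tables, because 9.4.1 still requires them on the CRF.

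**Working it through.** The plan gives no figure of its own here. The check compares the passages and then counts days.

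**1. Which rule applies to an event starting after day 30 in a Table 6 patient?**

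| Source | Event starting on days 31 to 105 |
|---|---|
| Table 6 footnote 12, first sentence | Not collected |
| Protocol 9.4.1 | Collected, any causality |
| Protocol 9.4.6 (non-serious AEs) | Collected |
| SAP 4.5.1 | Collected |
| Protocol 10.4.5.1 and SAP 5.9.1 | Counted as treatment-emergent |

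No passage says which rule prevails. The footnote's second sentence does not close the gap. It covers related events that last beyond day 105, but not unrelated events starting on days 31 to 105, nor related events that start and resolve within those days.

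**2. Size of the disputed interval**

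105 − 30 = 75 days (days 31 to 105); 75/105 = 71.4% of the post-dose window.

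**3. Share of the whole TEAE window**

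With dosing every 3 weeks, dose n falls on day 1 + 21(n − 1). The window runs from day 1 to the last dose day + 105. The maximum number of doses is 5 × 3 + 4 × 4 = 31.

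| Doses received | Last dose day | TEAE window (days) | Disputed share |
|---|---|---|---|
| 1 | 1 | 106 | 75/106 = 70.8% |
| 3 | 43 | 148 | 75/148 = 50.7% |
| 16 | 316 | 421 | 75/421 = 17.8% |
| 31 | 631 | 736 | 75/736 = 10.2% |

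These are calendar-day maxima, since new systemic therapy or retreatment can close the window sooner.

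**4. Scheduled visits inside the interval, for a completer**

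Table 6 places follow-up visit 1 at 28 days after the Cycle 9 visit and spaces later visits 28 days apart. It does not define the Cycle 9 visit, so both readings are shown.

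- Counted from the last dose (cycle 9 day 64): visits 1 to 4 fall on post-dose days 28, 56, 84 and 112. Two visits (2 and 3) lie in days 31 to 105.
- Counted from cycle 9 day 85, which is 21 days after the last dose: visits 1 to 4 fall on post-dose days 49, 77, 105 and 133. Three visits (1, 2 and 3) lie in the interval.

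On either reading, patients are seen while the two rules disagree on whether an AE is recorded.

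**5. Protocol 9.4.2**

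Take an SAE judged unrelated, at day 60, in a Table 6 patient. The opening sentence of 9.4.2 requires a report to the sponsor and 9.4.1 requires a CRF entry. The later 9.4.2 sentence excludes the report, and footnote 12 excludes collection. The later sentence may be a slip for events after day 105, as SAP 4.5.1 suggests, but that is an inference.

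**The case against.** The best reply is that footnote 12 is one outlier against a rule stated repeatedly in the safety chapter and the SAP, and that its own second sentence presupposes follow-up to day 105. Other text also limits the loss:

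- Protocol 9.4.1 requires AE enquiry at every patient contact, and Table 6 patients are seen about every 28 days.
- Protocol 9.4.3 requires accelerated reporting of Grade 3 or greater irAEs with no 30-day limit.
- Protocol 7.7 and footnote 11 require recording of drugs started in follow-up for study-drug-related AEs, which assumes those AEs are known.
- The AE row of Table 6 carries an arrow rather than a single mark at the first follow-up visit.

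Nothing shows that any site would follow the footnote, and the percentages are shares of days, not of events.

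Much of this stands as a limit on size. The exposed events are mainly lower-grade irAEs and AEs not judged related. The visits are chances to capture events as well as occasions for conflict, and their number is nominal: with the ±7-day windows, four could fall in the interval (for example, post-dose days 42, 63, 84 and 105).

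It does not remove the conflict. The footnote states an explicit 30-day stop, and staff working visit by visit will naturally consult the schedule footnotes. The end of the arrow is not legible in the text reviewed, and it cannot override that stop. Patients with progression may have fewer contacts after day 30, but no passage tells sites to stop recording their AEs at that point, so they fall outside this contradiction.

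**Conclusion.** The concern holds and should be fixed. For Table 6 patients, the protocol gives two incompatible collection rules for 75 of the 105 post-dose days. That is between 10.2% (31 doses) and 70.8% (1 dose) of the whole TEAE window, with the greatest weight on early stops, including those for toxicity. The figures assume dosing exactly every 3 weeks and no earlier end to the window.

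The textual conflict is certain. The bias is conditional: if some sites follow footnote 12, TEAE and serious TEAE counts would be too low, and unevenly so between sites. The number of events cannot be estimated, because the documents give no late-AE rate. Safety denominators, detection of deaths through survival follow-up, and ORR are not affected.

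The contradiction within 9.4.2 is equally clear, but it concerns reporting to the sponsor rather than the TEAE tables.

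**What to change.** - **Footnote 12:** reconcile it with the 105-day window in protocol 9.4.1, 9.4.6 and 10.4.5.1 and in SAP 4.5.1 and 5.9.1, so that collection covers the period the TEAE tables count.
- **Section 9.4.2:** reconcile the later sentence with the section's opening rule and with SAP 4.5.1, where the related-only rule starts after day 105.
- **Sites:** send a letter stating the single rule, and query events with onset on days 31 to 105 for Table 6 patients already off treatment. Do this before database lock, because unrecorded events become harder to recover later.
- **Related tidy-up:** the concomitant-medication window is 30 days in protocol 7.7 and Table 6 footnote 11 (apart from drugs treating related AEs) but 105 days in SAP 4.3. Reconcile these at the same time.

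The two AE corrections cost two wording changes in an amendment, a site letter and a limited set of queries. The medication window needs a further edit, either to 7.7 and footnote 11 or to SAP 4.3. If the longer window is kept, some retrospective medication collection may also be needed.
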